8.5.1 Pharmacokinetics

Pharmacokinetic parameters are not evaluated in this study.

8.5.2 Immunogenicity Assessments

Immunogenicity will not be assessed in this study.

8.5.3 Pharmacodynamics

Pharmacokinetic parameters are not evaluated in this study.

8.6 Human Biological Sample Biomarkers

Samples for biomarker research are required and will be collected from all participants in this study as specified in the SoA. Instructions for sample collection, processing, storage, and

shipment can be found in the separate laboratory manual provided to the sites.

For storage, re-use, and destruction of biomarker samples, see Section 8.5 and Appendix H.

8.6.1 Fractional Exhaled Nitric Oxide

Airway inflammation will be evaluated using a standardised single-breath FeNO test in accordance with the SoA. A single exhalation technique recommended by the manufacturer will be followed (Alving et al, 2017). The change from baseline in FeNO will be evaluated descriptively for association with OCS dose reduction during treatment with tezepelumab.

Participants will be asked whether they have had a respiratory infection in the 2 weeks prior to the measurement. The FeNO measurements will not be performed within 2 weeks of a respiratory infection. The FeNO test will be performed prior to spirometry. Participants should not eat or drink 1 hour prior to having the FeNO test. If not, the assessment should be postponed till after the required time has passed since the meal or drink or the visit must be rescheduled within the allowed visit window.

All post-Visit 2 FeNO assessments should be performed within \pm 2 hours of the time that the Visit 2 FeNO was performed.

8.6.2 Total Serum IgE and Specific IgE

Serum samples will be collected. The levels of total IgE and seasonal and perennial allergen-specific IgE will be tested by a central laboratory in accordance with the SoA (Table 1). Serum samples will be tested for seasonal and perennial specific IgE to identify subgroups of patients with sensitivities to these allergens. Primary and secondary endpoints may be evaluated in these subgroups. Serum samples will be tested for total IgE levels to descriptively evaluate their association with OCS-dose reduction during treatment with tezepelumab.

8.6.3 Peripheral Blood Eosinophils

Blood samples for the analysis of peripheral blood EOS will be analysed in a central laboratory as part of the routine haematology assessment (complete blood count) at timepoints specified in the SoA (Table 1). Blood samples will be tested to measure blood eosinophil counts. The blood eosinophil count at baseline will be used to define subgroups for evaluation of endpoints. In addition, the change from baseline in blood eosinophil count during the study will be used descriptively to evaluate an association with OCS-dose reduction during treatment with tezepelumab.

8.7 Optional Genomics Initiative Sample

Optional genomics initiative research is not applicable in this study.

8.8 Health Economics OR Medical Resource Utilisation and Health Economics

Health economics/Medical resource utilisation and health economics parameters are not evaluated in this study.

9 STATISTICAL CONSIDERATIONS

9.1 Statistical Hypotheses

The statistical analyses will be fully described in the SAP, as appropriate. Statistical analyses for this study will be conducted using SAS® v9.4 or latest version in a secure and validated area.

There is no predefined study hypothesis to test in this study, as such, no multiplicity control strategy will apply.

9.2 Sample Size Determination

The sample size for this study is based on the ability to provide sufficient precision in point estimates, both in the Full Analysis Set (FAS) and subsets for statistical analysis.

The primary outcomes variables, the proportion of participants who have discontinued OCS without loss of asthma control and the proportion of participants who reduced OCS dose to ≤ 5 mg/day without loss of asthma control. For the sample size estimation, a success rate of 50% is assumed. Estimate precision is expressed in a two-sided 95% CI distance from the point estimate of a 50% success rate to confidence limit for a total of approximately 300 participants. Calculations were conducted using the exact Clopper-Pearson CI formula for a single proportion in R v.4.0.1 (function *binom.test()* from *stats* package).

A total sample size of approximately 300 participants entering the induction phase is expected to provide 95% CIs for a single proportion extending approximately 5.8% from the point estimate of a 50% success rate. Estimates of the 95% CI of a > 50% success rate are incrementally smaller, as is shown in Table 12.

Table 12 Expected Distance Between Observed Proportion and Confidence Limit (Clopper-Pearson 95% CI Width)

Proportion of participants	Sample size					
Proportion of participants	50	100	150	200	250	300
50	± 14.5	± 10.25	± 8.3	± 7.1	± 6.4	± 5.8
60	-14.8 +13.6	-10.3 +9.7	-8.3 +7.9	-7.1 +6.8	-6.4 +6.1	-5.8 +5.6
70	-14.6 +12.1	-10.0 +8.8	-8.0 +7.2	-6.9 +6.3	-6.1 +5.6	-5.5 +5.1
80	-13.7 +10.0	-9.2 +7.3	-7.3 +6.1	-6.2 +5.3	-5.5 +4.8	-5.0 +4.4

The table also shows that the 95% CIs for subpopulation analyses as small as 50 are < 15% for proportions between 50% and 80%.

Note: The planned interim analysis does not impact the sample size calculation.

9.3 Populations for Analyses

The following statistical analysis sets will be defined:

9.3.1 All Participants Analysis Set

Comprises all participants screened for the study and will be used for reporting of disposition and screening failures.

9.3.2 Full Analysis Set

Includes all enrolled participants who received at least one dose of tezepelumab, irrespective of their protocol adherence and continued participation in the study. Participants will be analysed irrespective of whether they prematurely discontinue, according to the intent-to-treat principle. Participants who withdraw from the study will be included up to the date of their study termination. All efficacy, demographics, baseline characteristics, and safety analyses will be performed using the FAS.

Note: 'Enrolled' means a participant's, or their legally acceptable representative's, agreement to participate in a clinical study following completion of the informed consent process. Potential participants who are screened for the purpose of determining eligibility for the study, but are not assigned in the study, are considered 'screen failures', unless otherwise specified by the protocol.

9.3.3 Currently or Historically Elevated EOS Population

Includes participants who received at least one dose of tezepelumab and with peripheral blood EOS count of ≥ 150 cells/ μ L assessed by central laboratory at Visit 1 or documented EOS count of ≥ 300 cells/ μ L in the past 12 months. Participants will be analysed irrespective of whether they prematurely discontinue, according to the intent-to-treat principle. Participants who withdraw from the study will be included up to the date of their study termination. Primary efficacy analyses, key demographics, and baseline characteristics will also be presented using the currently or historically elevated EOS population in addition to the FAS.

9.4 Statistical Analyses

There will be 2 DBLs. The primary DBL will be carried out after approximately 300 participants have completed 28 weeks. All data available at that time may be analysed with the main focus on estimates of a subset of the pre-planned analysis outputs at Week 28. Further detailed description of the statistical analyses described in this section will be provided in the

SAP which will be developed and finalized before the first participant is enrolled. The final DBL will be conducted once the last participant has completed the safety follow-up visit (Week 64) with the main focus on estimates on Week 52 (EOT).

Details regarding both database locks will be provided in the DMP which will be developed and signed off prior to the first patient enrolled.

9.4.1 General Considerations

No formal hypothesis will be tested in this study, and no multiplicity adjustment will be applied in the statistical analysis. No imputation will be performed beyond the approach defined for outcome measures. Imputation for partial date will be detailed in the SAP document.

In general, the last measurement at or prior to Visit 2 will serve as the baseline measurement. If there is no value at or prior to Visit 2, then the baseline value will not be imputed and will be set to missing.

The baseline OCS dose is derived as the most recent prescribed, daily maintenance OCS dose prior to Visit 2 (ie, the daily dose regimen that a participant is prescribed at the time of Visit 2). If the OCS dose is administered every other day, the total OCS dose over the 2 days will be summed and averaged.

Further details regarding baseline definitions will be provided in the SAP.

Absolute change from baseline is defined as *(post-baseline value – baseline value)*. The percent change from baseline is defined as *{(post-baseline value – baseline value)*baseline value)*100%*.

Frequency and percentages of participant disposition and reasons for discontinuation of IP will be presented. Participants who prematurely discontinue the IP will be listed along with the reason for discontinuation. In addition, frequency and percentages of withdrawal from the study together with reasons will be presented.

Demographics and participant characteristics will be summarised using frequency counts and percentages (for categorical variables) and n, mean, standard deviation, median, minimum and maximum (for continuous variables) using the FAS.

Relevant medical history/current medical conditions will be summarised by System Organ Class (SOC) and Preferred Term (PT) of the Medical Dictionary for Regulatory Activities (MedDRA) dictionary using frequency counts and percentage of participants in the FAS.

Prior and concomitant medications, categorised according to the WHO Drug Dictionary which employs the Anatomical Therapeutic Chemical classification system, will be summarised as frequency counts and percentage of participants reporting usage. Prior medications are defined as those which stopped before first dose of IP. Concomitant medications are defined as those which either started or continued after first dose of IP.

Important protocol deviations will be defined prior to first participants enrolled. Participants will not be excluded from analysis sets on the basis of any important protocol deviations. The definitions of each category of important protocol deviation will be fully specified in the SAP. Details regarding statistical analysis will be provided in the SAP. In general, continuous endpoints will be summarised using the mean, the standard deviation, median, minimum value, and maximum value, and the categorical endpoints will be summarised using frequency counts and percentages. Two-sided 95% CI for proportions computed using exact Clopper-Pearson method may also be presented. Time to event data will be presented graphically using Kaplan Meyer curve.

In general, all data up to Week 28 or Week 52 will be included in the analysis, even if a participant discontinues treatment or changes background therapy other than OCS (treatment policy strategy). If a participant initiates therapy with other biologic for treatment of asthma, then only data collected up until the initiation of the other biologic treatment will be included in the analysis (hypothetical strategy).

In general, efficacy analyses will be based on planned treatment period, starting on the date of first dose of IP and ending on the date of the Week 28 or Week 52 visit or earlier study withdrawal date.

Safety analyses will be based on-treatment and/or on-study period. Details will be specified in the SAP. On-treatment period starts on the date of first dose of IP and ends on minimum (date of last dose of IP + 33 days, date of death, date of study withdrawal). On-study period (planned treatment and follow-up) starts on the date of first dose of IP and ends on the study completion or withdrawal date. Data will be listed in participant-level data listings.

9.4.2 Global/Country Situation Considerations, Including COVID-19

Descriptive summaries to assess global/country situation impacts will be provided for evaluating visits impacted (missing visits, type of visits), exposure impacts, and AEs. Additional descriptive analyses may be needed to evaluate the impact of the global/country situation on this trial and its endpoints. Further details will be included within the SAP document.

9.4.3 Efficacy

9.4.3.1 Primary Endpoints

The following outcomes are designed to support the primary objective of the study:

- Proportion of participants who discontinue OCS without loss of asthma control
- Proportion of participants who reduce OCS dose to ≤ 5 mg/day without loss of asthma control

The baseline OCS dose is defined in Section 9.4.1. The final OCS dose is defined based on the prescribed maintenance dose, expressed as a dose per day, at Week 28 or Week 52. If the participant is on a fixed daily dose, then the OCS dose is defined as that prescribed dose. If the participant is on every other day regimen, then the OCS dose is defined as the average amount prescribed to be taken each day. Final daily OCS dose will be derived as described in Table 13. Further details may be specified in the SAP.

Table 13 Final Daily Maintenance OCS Derivation

Situation	Final daily maintenance OCS dose
Initiation of therapy with another biologic for treatment of asthma	Last reported OCS dose ^a received by participant with asthma stability verified ^b prior to initiation of another biologic.
Premature withdrawal from the study	Last reported OCS dose ^a received by participant with asthma stability verified ^b at the time of study withdrawal.
Any other situation	Last reported OCS dose ^a received by participant with asthma stability verified ^b

^a daily OCS dose is based on information collected in ECSYSCRT eCRF.

Each primary endpoint will be summarised by number and proportion (with 95% CI) of participants. The 95% CIs for proportions will be calculated using the Clopper-Pearson exact method.

Analysis of the primary endpoints will be based on both the FAS population and the current or historical elevated EOS population. In addition, primary endpoints will be summarised by pre-specified subgroups using FAS population including (but not limited to):

- Baseline EOS group: $< 300/\mu L$, $\ge 300/\mu L$
- Baseline EOS group: $< 150/\mu L, \ge 150/\mu L$.

Any further requirements for subgroups analysis and exact definition of all relevant categories where needed, will be pre-specified in the SAP.

^b Asthma stability is defined as no change in OCS dose for at least 2 weeks.

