To describe participant satisfaction with change in daily OCS use	Change from baseline in Participant Perception of OCS (PPOCS) score at Week 28 and Week 52
To evaluate the ability of tezepelumab to reduce exposure to SCS	Mean daily exposure of systemic corticosteroids (mg/day) taken for asthma reasons over 28 and 52 weeks

a. Loss of asthma control is defined as asthma worsening or exacerbation. Asthma worsening will be defined by an increase of ACQ-6 score ≥ 0.5 from baseline (see Section 8.1.2.1). Asthma exacerbation will be defined by worsening of asthma symptoms that leads to temporary bolus/burst of systemic corticosteroids (or a temporary increase in stable OCS background dose) for at least 3 consecutive days (a single depo-injectable dose of corticosteroids being considered equivalent to a 3-day bolus/burst of systemic corticosteroids), and/or an ER or urgent care visit requiring systemic corticosteroids, and/or inpatient hospitalisation, both due to asthma (see Section 8.1.3).

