- A temporary bolus/burst of systemic corticosteroids (or a temporary increase in stable OCS background dose) for at least 3 consecutive days to treat symptoms of asthma worsening; a single depo-injectable dose of corticosteroids will be considered equivalent to a 3-day bolus/burst of systemic corticosteroids.
- An ER or urgent care visit (defined as evaluation and treatment for <24 hours in an emergency department or in an urgent care centre) due to asthma that required systemic corticosteroids (as per the above).
- An in-patient hospitalisation (defined as admission to an inpatient facility and/or evaluation and treatment in a healthcare facility for ≥ 24 hours) due to asthma.

After recovery from the first exacerbation or asthma deterioration, the participant will be allowed to proceed with another attempt to reduce OCS dose; however, this must follow a lower speed of OCS down-titration (reductions Q4W). In case of a second exacerbation or asthma deterioration, no further OCS dose reduction will be allowed, and the participant will continue on the same OCS dose or will return to a one-step higher dose level (or more as considered necessary by the investigator). The new OCS dose established after a second asthma exacerbation or deterioration will be maintained until Week 52. Further details are provided in Sections 6.5.1.1 and 8.1.3.

4. **Follow-up (Week 64):** A follow-up contact (phone call) will be scheduled at Week 64 or 16 weeks (\pm 5 days) after the last dose of tezepelumab.

All participants who prematurely discontinue tezepelumab or discontinue from the study should return to the study site and complete the procedures described for the IPD visit within 4 weeks (\pm 7 days) after the last dose of tezepelumab. In addition, participants who prematurely discontinue tezepelumab will be encouraged to remain in the study and complete all subsequent scheduled study visits, procedures, and assessments through study completion (see Section 7.1).

An interim analysis may be performed if approximately 50 participants complete Visit 4 before a data cut-off date planned on mid-April 2023.

There will be 2 DBLs. The primary DBL will be carried out after approximately 300 participants having completed 28 weeks. All data available at that time may be analysed with the main focus on estimates of a subset of the pre-planned analysis outputs at Week 28. The final DBL will be conducted once the last participant has completed the safety follow-up

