² A single depo-injectable dose of corticosteroids will be considered equivalent to a 3-day bolus/burst of systemic corticosteroids.

In the case of a second event of asthma deterioration or exacerbation, the OCS reduction will be stopped, and the participant will continue on the same OCS dose or will return to a one-step higher dose level (or more as considered necessary by the investigator).

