To describe the ability of tezepelumab to improve Sino-nasal Outcome Test (SNOT-22)	Change from baseline in Sino-nasal Outcome Test (SNOT-22) at Week 28 and Week 52
	• Proportion of SNOT-22 responders at Week 28 and Week 52
To describe participant satisfaction with change in daily OCS use	Change from baseline in Participant Perception of OCS (PPOCS) score at Week 28 and Week 52
To evaluate the ability of tezepelumab to reduce exposure to SCS	Mean daily exposure of systemic corticosteroids (mg/day) taken for asthma reasons over 28 and 52 weeks

^a Loss of asthma control is defined as asthma worsening or exacerbation. Asthma worsening is defined by an increase of ACQ-6 score ≥ 0.5 from baseline. Asthma exacerbation is defined by worsening of asthma symptoms that leads to temporary bolus/burst of systemic corticosteroids (or a temporary increase in stable OCS background dose) for at least 3 consecutive days (a single depo-injectable dose of corticosteroids being considered equivalent to a 3-day bolus/burst of systemic corticosteroids), and/or an ER or urgent care visit requiring systemic corticosteroid, and/or inpatient hospitalisation, both due to asthma. ^b The AIRQ questionnaire is not assessed at Week 28 and the objective is analysed at Week 52 only (see Section 2).

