- Or, an ER or urgent care visit (defined as evaluation and treatment for <24 hours in an emergency department or in an urgent care centre) due to asthma that required systemic corticosteroids (as per the above).
- Or, an in-patient hospitalisation (defined as admission to an inpatient facility and/or evaluation and treatment in a healthcare facility for ≥ 24 hours) due to asthma.

After recovery from the first exacerbation or asthma deterioration, the participant is allowed to proceed with another attempt to reduce OCS dose; however, this must follow a lower speed of OCS down-titration. In case of a second exacerbation or asthma deterioration, no further OCS dose reduction is allowed, and the participant continues the same OCS dose or return to a one-step higher dose level (or more as considered necessary by the investigator). The new OCS dose established after a second asthma exacerbation or deterioration is maintained until Week 52. Further details are provided in the CSP.

4. **Follow-up (Week 64):** A follow-up contact (phone call) is scheduled at Week 64 or 16 weeks (± 5 days) after the last dose of tezepelumab.

Figure 1 Study Design flow chart

All participants who prematurely discontinue tezepelumab or discontinue from the study should return to the study site and complete the procedures described for the premature IPD visit within 4 weeks (\pm 7 days) after the last dose of tezepelumab. In addition, participants who prematurely discontinue tezepelumab are encouraged to remain in the study and complete all subsequent scheduled study visits, procedures, and assessments through study completion (more details in CSP Section 7.1).

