4.2.1.1 Definition

The following primary endpoints are designed to support the primary objective of the study:

- Proportion of participants who discontinue OCS without loss of asthma control
- Proportion of participants who reduce OCS dose to ≤ 5 mg/day without loss of asthma control

Both proportions are assessed at Week 28 and at Week 52.

4.2.1.2 **Derivations**

The baseline OCS is defined in Section 3.3.1.2. The final OCS dose at Week 28 (Visit 9) or at Week 52 (Visit 15) is defined as in Section 3.3 and Table 4. Strategies of handling intercurrent events are presented in Section 4.2.

Table 4 Final daily maintenance OCS derivation

Situation	Final daily maintenance OCS dose
Initiation of therapy with another biologic for treatment of asthma	Last reported OCS dose ^a received by participant with asthma stability verified ^b prior to initiation of another biologic for treatment of asthma.
Premature withdrawal from the study	Last reported OCS dose ^a received by participant with asthma stability verified ^b at the time of study withdrawal.
Any other situation	Last reported OCS dose ^a received by participant with asthma stability verified ^b

^a daily OCS dose is based on information collected in ECSYSCRT eCRF.

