4.2.1.5 Sensitivity Analyses of the Primary Endpoint

No sensitivity analysis.

^b Asthma stability is defined as no change in OCS dose for at least 2 consecutive weeks.

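### The primary endpoints are labelled as OCS reduction without loss of asthma control, but their derivation requires only a 2-week stable dose and never uses ACQ-6

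*Protocol*

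**What the plan says.** **Label.** SAP 4.2.1.1 names the first primary endpoint "Proportion of participants who discontinue OCS without loss of asthma control". The second carries the same condition for a dose of 5 mg/day or less, and Protocol 9.4.3.1 agrees on both.

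**Meaning of the label.** Protocol Section 3, Table 2 footnote a: "Loss of asthma control is defined as asthma worsening or exacerbation". SAP 1.1, Table 1 footnote a: "Asthma worsening is defined by an increase of ACQ-6 score ≥ 0.5 from baseline".

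**Derivation.** Protocol Table 13 and SAP Table 4 take the last reported OCS dose at which asthma stability was verified. Protocol footnote b: "Asthma stability is defined as no change in OCS dose for at least 2 weeks". SAP footnote b: "Asthma stability is defined as no change in OCS dose for at least 2 consecutive weeks". The dose comes from one eCRF page, ECSYSCRT.

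**Conduct.** Protocol 8.1.2.1 says that after a second deterioration or exacerbation tapering stops and "the participant will continue on the same OCS dose or will return to a one-step higher dose level". Protocol 4.1 adds: "The new OCS dose established after a second asthma exacerbation or deterioration will be maintained until Week 52". SAP 1.2 repeats this. Protocol 8.1.1 also lets the investigator raise the maintenance dose.

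**Other analyses.** SAP 4.2 plans no sensitivity analysis. The one supplementary analysis (SAP 4.2.1.6) restricts to on-treatment data and adds no control criterion.

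**The concern.** The term asthma stability in the two derivation tables reads as if it carried out the control condition in the endpoint name. Its footnote defines it by dose alone. An unchanged dose shows control only if loss of control always changes the dose, and the conduct rules do not require that.

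The trial tests no hypothesis (Protocol 9.1), so the reported proportion and its meaning are the result. As planned, a reader would take both primary proportions as control-verified when ACQ-6 was never checked. ACQ-6 and exacerbations are summarised in separate tables, so the joint proportion cannot be read off the planned summaries.

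**Working it through.** **1. Definition against derivation**

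| Component of loss of control | Used in Table 13 / Table 4? |
|---|---|
| ACQ-6 rise of 0.5 or more from baseline | No. No step in SAP 3.3 or 4.2.1 refers to ACQ-6 when setting success |
| Exacerbation | Unclear (step 3) |

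**2. A case that follows the plan's own rules.** A participant is on 2.5 mg/day. A second ACQ-6 deterioration occurs at Week 24. The dose is kept the same, as Protocol 8.1.2.1 allows. ACQ-6 is 0.8 above baseline at Weeks 26 to 28, and no burst is given. The dose has been unchanged for at least 2 weeks and is at or below 5 mg/day, so the participant is a Week 28 success on the second primary endpoint. By Table 2 footnote a, asthma control is lost.

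**3. Exacerbations.** The exacerbation definition includes a temporary rise in background OCS for at least 3 days, which could be read as a dose change. SAP 3.3 leaves doses given for worsening or exacerbation out of the daily dose. It also says that when such doses overlap with maintenance doses, the latter are excluded. It does not say what dose then applies on those days, or whether the 2-week run is broken. The text does not settle whether the derivation catches exacerbations.

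**4. Direction.** Adding a condition to the success rule can only remove successes.

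**5. The plan's own figure.** The exact Clopper-Pearson interval for 150/300 is 44.2% to 55.8%, or 5.80 points either side. This reproduces the 5.8 in Protocol 9.2 and SAP 1.3.

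**6. Illustration of size.** The documents do not give the share *f* of dose-rule successes who have lost control, so *f* is an assumption. New proportion = successes × (1 − *f*) / 300, with successes rounded to a whole number. Three participants are 1 point.

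| Starting rate | *f* | Successes left | Proportion (95% CI) |
|---|---|---|---|
| 150/300 = 50.0% (44.2 to 55.8), planning rate | 2% | 147 | 49.0% (43.2 to 54.8) |
| | 5% | 142 | 47.3% (41.6 to 53.2) |
| | 10% | 135 | 45.0% (39.3 to 50.8) |
| 186/300 = 62.0% (56.2 to 67.5) | 10% | 167 | 55.7% (49.8 to 61.4) |
| 243/300 = 81.0% (76.1 to 85.3) | 10% | 219 | 73.0% (67.6 to 77.9) |

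The 62% and 81% are the rates Protocol 2.1 quotes from an earlier open-label trial of another biologic. The endpoint behind the 81% is worded differently, so both are only reference points.

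**7. When the shift exceeds the lower CI half-width.** Half-width × 300 gives 5.80 points = 17.4, so 18 of 150 (12.0%). It gives 5.76 points = 17.3, so 18 of 186 (9.7%), and 4.90 points = 14.7, so 15 of 243 (6.2%).

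**The case against.** The strongest defence is that control is enforced during conduct. Protocol 4.1 and 8.1.2.1 make each further reduction depend on ACQ-6 and exacerbations, so a participant who reaches a low dose has mostly been controlled on the way down. On this view the 2-week stable dose is a pre-specified, if weak, stand-in for control. This stands as a limit on size. It does not close the gap: the rules stop further tapering but do not undo a dose already reached, and the increase in Protocol 8.1.1 is discretionary.

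Three stronger readings are tempting, and the documents do not support them.

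- *That exacerbations are ignored too.* SAP 3.3 and the exacerbation definition leave room for a burst or temporary increase to break the 2-week run. Only the ACQ-6 half is established.
- *That the sponsor concedes the gap by leaving the control wording out of the interim summary (SAP 4.2.1.8).* That section says the Table 4 derivation cannot be applied so early in follow-up. The wording goes because the stability rule goes.
- *That the endpoint of 50% or greater reduction has the same fault.* It belongs to a separate secondary objective. That objective mentions control, but the endpoint's own text sets no control condition.

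Protocol 9.4.1 also plans participant-level listings, so the joint result could be rebuilt by hand. It is missing only from the summary tables.

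**Conclusion.** The label is wrong as written. Neither primary endpoint's derivation uses ACQ-6, so a participant with lost control by the protocol's own definition can count as a success at Week 28 or Week 52. For exacerbations this is possible but not shown.

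The error can only be upward. Its size is unknown and may be modest. At the planning rate, 10% of successes reclassified costs 5.0 points, and 12.0% is needed before the shift exceeds the lower half-width. These figures rest on 300 participants and an assumed share.

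A reader might infer that the main definition has to be replaced. The documents do not compel that. SAP edition 5.0 is dated 9 November 2023, after the planned mid-April 2023 interim cut-off, and changing the main rule that late in an open-label trial carries a credibility cost of its own. An accurate label and a pre-specified companion analysis are enough. This should be fixed, although no formal decision depends on it.

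**What to change.** 1. **Keep the Table 13 / Table 4 dose rule.** Label its result as a dose threshold met with a 2-week stable dose, not as control-verified.
2. **Add a control-verified proportion to SAP 4.2.1.6**, for both primary endpoints at Weeks 28 and 52. Success needs the dose threshold, a last ACQ-6 less than 0.5 above baseline, and no exacerbation on the EXACA form started or ongoing.
3. **Assess control over the same 2-week stable-dose period that sets the final dose**, so that dose and control refer to the same time. If the run is longer, state which 14 days apply. The last 14 up to the visit, study withdrawal or start of another biologic would be our choice; the documents set none. Fourteen days normally hold two weekly scores (target day = week × 7 + 1, so days 190 and 197, or 358 and 365).
4. **Missing scores.** Count dose-successes with no ACQ-6 in that period, or no baseline ACQ-6, as not meeting the control-verified endpoint. Report their number, and show the result judged on exacerbations alone as the upper bound. The two differ by 1 point per 3 such participants who pass on exacerbations. Follow-up option 3 in Protocol 7.1 collects no ePRO data, so this matters most at Week 52. State whether the fallback baseline in Protocol 8.1.2.1 applies here, because that section bars it from the ACQ-6 analysis.
5. **SAP 3.3.** State whether a burst interrupts the 2-week run.
6. **Secondary OCS endpoints.** Keep the 50% or greater and the categorised endpoints on the same dose-only basis. Categories 1 to 3 together are the 50% or greater group, so conditioning only one would make the two tables disagree. Remove or qualify the clause about maintained control in SAP 4.2.6.2.

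**Cost.** Text edits, one extra table and some programming, with a possibly lower figure beside the main one. No new data: weekly ACQ-6 and exacerbation dates are already collected.
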